## **Abstract**

*Background:* The impact of COVID-19 has been unequal across the nation in regards to number of cases, hospitalizations and deaths. Notably, primary strategies employed for COVID-19 mitigation at the national, state, and local levels (i.e. COVID-19 testing, vaccination rollouts, etc) often have inadequate reach in communities that experience COVID-19 disparities. Therefore, new approaches for COVID-19 mitigation are needed to more effectively reduce disparities. The current trial tests a novel approach by evaluating the efficacy of the Nurse-Community-Family Partnership (NCFP) intervention to improve primary (COVID-19 testing uptake) and secondary (COVID-19 vaccine uptake, adoption of COVID-19 infection control measures, household mutual aid capacity, and seasonal influenza vaccine uptake) outcomes in a community experiencing disproportionate COVID-19 morbidity, mortality, and barriers to mitigation.

*Methods:* In this two-arm parallel randomized control trial, we will evaluate the efficacy of the NCFP intervention in improving the primary and secondary outcomes. We will recruit 150 households from the Bronx in New York City. These households will be randomized in a 2:1 ratio, intervention:control, using a computer-generated algorithm. The NCFP intervention will take place over 5 months. The core components of the intervention include regular home visits by nurses and community health workers, development of a household-specific infection control plan, offer of at-home COVID-19 tests, and navigation to COVID-19 vaccination and other ancillary services. NCFP intervention components and intensity is informed by a household risk algorithm (low, medium, high). All households will complete a baseline assessment, monthly follow-up surveys during months 1-6 post baseline, and a delayed 9-month follow-up survey. We will use intent-to-treat analysis to evaluate the efficacy of the intervention in improving the primary and secondary outcomes compared to the standard of services. Subgroup analyses based on select household characteristics will be conducted.

*Discussion:* The NCFP intervention may have utility for mitigating COVID-19 at the household level—a novel and promising approach. If the trial achieves this, this care delivery model relying on a partnership between nurses, community health workers, and families will expand the available cadre of effective strategies for COVID-19 mitigation in underserved communities.

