### **Methods in analysis to handle protocol non-adherence and any statistical methods to handle missing data {20c}**

This trial will follow a per-protocol analysis to address non-adherence. We will analyze the results using both the intent-to-treat and per protocol analysis approaches. We will use the intent-to-treat approach when reporting the results. In addition, we will pursue the per protocol approach for sensitivity analysis.

In some analyses, there is likely to be missing data due to a respondent not answering a question. In general, this occurs infrequently, but occasions may arise where missing data must be formally dealt with. Data can be missing at random (MAR), missing completely at random (MCAR) or missing in a systematic way that precludes application of simple methods of missingness, such as the Expectation-Maximization (EM) methods. To gain perspective on the nature of the missingness for a given variable, we will create a dummy variable coded for each respondent as 1 = has a missing value on the variable in

question and 0 = does not have a missing value, and then test for associations between these variables and other variables in the models. We will also apply Little's multivariate test for MCAR. Ideally, missingness will not be related to other variables. Missing data also can result from study attrition. We will differentiate these two sources of missingness and explore the dynamics of each. We will approach missing data using either Full Information Maximum Likelihood methods, multiple imputation methods or systematically model missing data bias, depending on the nature of the data and the models being evaluated.

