A Nurse-Community Health Worker-Family Partnership Model: Addressing Uptake of COVID-19 Testing and Control Measures

Statistical Analysis Plan (SAP)

Unique Protocol ID: 3P30DA011041-23S1

Protocol Version: 1.1

NCT #: NCT04832919

Document Date: 07/12/22

Contributors:

[name] – Senior Biostatistician

[name] – Junior Research Scientist/Data Manager

STATISTICAL DESIGN AND POWER

Measures.

Definition of Primary Outcomes

Household COVID testing uptake at the 9-month follow up is one of the main primary outcomes of interest. The investigative team will document all medical services administered by nurses during home visits, as well as self-reported information regarding COVID-19 testing uptake by study participants in the treatment and control groups. Participants will be asked whether they have received COVID-19 testing in the past three months [Yes/No]. Additionally, variables collected via the COVID-19 Symptoms, Diagnoses, and Testing Scale are the primary outcomes. This questionnaire is adapted from the COVID-19 Cannabis Health Questionnaire (CCHQ) (Vidot et al, 2020) and will measure COVID-19 symptoms, diagnoses, and testing. At the 9-month follow up point, participants will be asked questions regarding whether they are currently sick with an illness that might be related to COVID-19, any symptoms the participant experienced in the past three months [Check All That Apply], and the result of the participant's last COVID-19 test [Positive/Negative].

Definition of Secondary Outcomes

For the randomized trial, data collected utilizing the following questionnaires are secondary outcomes:

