There are several mediating variables of interest including: knowledge and self-efficacy for COVID-19 prevention, testing salience, habitual processes, and medical mistrust. These measures are captured in the baseline, 6-month, and 9-month questionnaires. **Figure 2** features all mediating variables considered for these analyses.

Created Variables

We will create summary scores for all survey scales using validated scoring procedures. We will create difference variables (e.g., 6 month-baseline, 9 month – 6 month, 9 month-baseline) for time varying variables (e.g., vaccination status, COVID-19 exposure, employment status) measured at multiple time points.

Figure 1: Consort Flow Diagram

[figure not shown]
[figure not shown]

Figure 2: NCFP Theoretical Model

Design.

The randomized control trial will include 150 households, and 400 individual household members who will be randomized into 2 arms with parallel assignment in a 2:1 ratio, intervention:control. Participants in the intervention arm will receive the Nurse-Community Health Worker-Family Partnership intervention. The control arm will receive standard access to NYC Department of Health COVID-19 testing sites and standard COVID-19 public health messaging for NYCHA residents.

Framework.

With regard to hypothesis testing, the trial will utilize a superiority hypothesis testing framework. The study team will compare differences between baseline data and data collected at the 9-month follow-up timepoint to assess whether or not the intervention group had a higher efficacy in regards to the outcomes of interest than that of the control group.

Randomization.

After the baseline assessment and confirmation of eligibility, treatment allocation will be determined using a household-level randomization scheme of 2:1. The study team will randomize households using the password-protected REDCap desktop app using a predetermined randomization algorithm entered into the EDC system.

Interim Analyses.

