$$y_{tij} = \ln\left(\frac{\pi_{tij}}{1 - \pi_{tij}}\right) = B_0x_{0ij} + \beta_1x_{tij} + \beta_2x_{ij} + \beta_3x_j + \varepsilon_{i(j)}^{(2)} + \varepsilon_j^{(3)}$$

For continuous outcomes, we will use a random-intercepts multilevel regression model, for each timepoint t , individual i , that is a member of household j . The basic equation will follow the form:

$$y_{tij} = B_0x_{0ij} + \beta_1x_{tij} + \beta_2x_{ij} + \beta_3x_j + \varepsilon_{i(j)}^{(2)} + \varepsilon_j^{(3)}$$

A random-intercepts model will give the conditional assessment of the extent to which household-level exposures vary on the outcomes after taking into account individual-level exposures, assuming the household-level variation is normally and independently distributed with a constant variance. Where y_{tij} represents the outcome for the i^{th} individual that resides in household j and time t , x_{tij} denotes the vector of time-varying covariates (e.g., exposure to COVID-19, household member exposed, household member infected), x_{ik} denotes the vector of individual-level variables (e.g., age, gender, race, ethnicity, comorbidities), and x_k is a vector of household-level variables (e.g., household plan developed). The vector of regression coefficients for the time-varying variables is denoted as β_1 ; similarly, β_2 denotes the vector of regression coefficients for the individual-level variables, and β_3 denotes the vector of regression coefficients for the household-level variables.

The random effect for individual i that is a member of household j is denoted by $\varepsilon_{i(j)}^{(2)}$, and $\varepsilon_j^{(3)}$ denotes the random effect for the third (household-level) cluster. We assume the random effects are independent and normally distributed [5-7]. The variance partitioning coefficient (VPC), or the amount of variability in the outcome attributed to predictors at each level, will be calculated. This will tell us to which extent household level and individual-level variables contribute to the outcome allowing for an examination of the impacts of COVID-19 at multiple levels. In order to examine these impacts, a test for the difference in two proportions using a mixed-effects regression model based on a clustered 3-Level Hierarchical Design with level-3 (household) randomization will be utilized.

Mediation, moderation, and mediated moderation, moderated mediation analyses

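### The SAP's Aim 4 model equations write neither arm nor visit and name post-randomisation covariates, and no sentence keeps those covariates out of the intent-to-treat estimate

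*SAP*

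**What the plan says.** **The model.** The SAP's Longitudinal Analysis gives one form for binary and one for continuous outcomes. Each has an intercept, three covariate vectors (time-varying, individual, household) and random intercepts for person and household. Arm and visit are neither written out nor given as examples. The first vector "denotes the vector of time-varying covariates (e.g., exposure to COVID-19, household member exposed, household member infected"; the last "is a vector of household-level variables (e.g., household plan developed". Under Created Variables the SAP speaks of "time varying variables (e.g., vaccination status, COVID-19 exposure, employment status) measured at multiple time points", so exposure is not only a baseline value.

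**The arm comparison.** The same section closes with "a test for the difference in two proportions using a mixed-effects regression model based on a clustered 3-Level Hierarchical Design", randomised by household, and lists no covariates for it. Under Framework the team will "compare differences between baseline data and data collected at the 9-month follow-up timepoint" between arms. Of the outcome the SAP says: "Household COVID testing uptake at the 9-month follow up is one of the main primary outcomes of interest".

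**Predictors.** Predictor Variables names COVID-19 exposures as the main predictor. Analysis for Aim 4, and the protocol's statistical methods {20a}, name intervention group as a key predictor in the bivariate analyses. Analysis for Aim 4 then places predictors, mediators and moderators together in the multilevel models for testing uptake.

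**The estimand.** The protocol abstract states "We will use intent-to-treat analysis to evaluate the efficacy of the intervention", and section {20c} states "We will use the intent-to-treat approach when reporting the results".

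**The concern.** A covariate affected by treatment does not belong in a model whose arm coefficient is to be read as the intent-to-treat effect. The only household-level example in the SAP's model is of this kind. The protocol's intervention description {11a} puts a tailored household infection control plan first in the standard intervention content. The treatment-as-usual section offers controls information about community sites and standard health-department material, and no plan. The SAP's own mediation section assumes that the intervention acts on the mediators and moderators as well as on the outcome, yet mediators are also placed in the primary-outcome models.

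At stake is the primary estimate. Two analysts could both follow the SAP, one fitting arm alone and the other fitting arm with the covariates it names. They would report different results, and only the first would have the effect that the protocol promises.

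**Working it through.** **Inputs from the SAP's Power and Sample Size section.** Testing 0.25 vs 0.10; 100 vs 50 households; 2 people per household; 3 timepoints; correlation bounds 0.7 (within person) and 0.3 (within household); alpha 0.05, two-sided under Final Analysis.

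**Assumed, because the documents give no figure.** Plan uptake of 80% or 90% in the intervention arm and none in controls; the share of the effect acting through the plan; exposure rates and the strength of the exposure-testing link.

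**1. The plan's own figure.** Design effect = 1 + (3-1)(0.7) + 3(2-1)(0.3) = 3.3. Effective n = 600/3.3 = 181.8 and 300/3.3 = 90.9. Power is 80.6% (Wald test on the log odds ratio), 86.4% (pooled two-proportion) or 91.6% (unpooled). The stated figure of more than 80% reproduces for an effect common to three timepoints. For 9 months alone the design effect is 1.3, effective n is 153.8 and 76.9, and the same three formulas give 73.8%, 79.6% and 86.6%. A simulated random-intercept logistic model gives about 80-84%. The figure therefore depends on which contrast is meant.

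**2. Plan in the model, half the effect acting through it.** Once the plan is a covariate, arm is estimated from intervention households without a plan against controls. With no selection into having a plan, those households test at 0.10 + 0.15/2 = 0.175. Plan households then test at (0.25 - 0.2 x 0.175)/0.8 = 0.269 at 80% uptake, which keeps the arm total at 0.25. The arm coefficient is 0.175 - 0.10 = 0.075, not 0.15, and is the same at 90% uptake. A simulation (4,000 trials per scenario, linear model with household-clustered errors) gives 0.149-0.151 with arm alone and 0.075 with the plan added.

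**3. Plan in the model but inert.** On the log-odds scale at 9 months:
- Arm alone: variance = 1/(153.8 x 0.1875) + 1/(76.9 x 0.09) = 0.0347 + 0.1444 = 0.1791.
- 80% uptake: the first term becomes 0.0347/0.2 = 0.1733, the total 0.3178, and the SE ratio sqrt(0.3178/0.1791) = 1.33.
- 90% uptake: 0.0347/0.1 = 0.3467, the total 0.4911, and the ratio 1.66.

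Simulation of the mixed logistic model gives 1.36 and 1.72. An equal-variance linear model gives larger ratios, sqrt(2.33) = 1.53 and sqrt(4.00) = 2.00. The logistic figures are used here because that is the planned model.

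**4. Plan in every intervention household and no control household.** Plan and arm are then the same column, and the arm effect cannot be estimated.

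**5. Follow-up exposure in the model.** Take 30% exposed in controls, an exposure-testing odds ratio of 2 to 5 in both arms, and arm margins fixed at 0.25 and 0.10. Standardised to the control exposure rate, the risk difference is 0.150 if exposure is equal in the two arms, 0.164-0.184 if 20% of the intervention arm is exposed, and 0.095-0.124 if 50% is. The shift can go either way, and is nil when arm does not change exposure.

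**6. One arm coefficient shared with baseline rows.** If the three timepoints are baseline, 6 and 9 months, with differences of 0, 0.15 and 0.15, the average is (0 + 0.15 + 0.15)/3 = 0.10.

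**The case against.** The SAP calls its formula basic and introduces the covariates as examples. Arm would fit the household vector and visit the time-varying one. The formula also serves variance partitioning, and the arm test is a closing sentence with no covariates attached. Intervention group is a key predictor in both documents. Multilevel models at each time point are already planned, so a 9-month-only model exists. Mediators also have their own structural equation analyses, and components received is a listed sensitivity analysis. All of this stands. It rules out the reading that the SAP omits an arm test. It does not say which covariates that test may contain.

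Other stronger readings are not supported:
- *Exposure is tied to the primary outcome by design.* In the intervention arm a reported exposure does lead to a test offer. But the intervention lasts 5 months and the 9-month item looks back three months, so this link bears mainly on the 6-month outcome.
- *Any change in the odds ratio on adjustment is bias.* It is not. For 0.25 vs 0.10 the marginal odds ratio is 3.0, but with a household correlation of 0.3 the household-conditional one is already about 4.5-5.3 before any covariate is added. Risk differences are used above for this reason.
- *The SAP demotes intent to treat.* It mentions it only among sensitivity analyses, but the protocol commits to it twice.
- *The trial is underpowered.* Step 1 does not show this.

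**Conclusion.** The point holds as a gap in specification. The SAP does not say how arm and visit enter the Aim 4 model, names an intervention component and follow-up exposure or infection as covariates, and has no rule confining adjustment to baseline values. If the named covariates enter the arm-effect model, its arm coefficient is not the intent-to-treat effect, unless arm leaves those covariates unchanged or they have no bearing on testing.

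The size is illustrative only. Halving of the risk difference to about 0.075 rests on 80-90% plan uptake, none in controls, half the effect acting through the plan and no selection into having one. With selection, the direction of bias is not fixed. The SE increase of about 1.3 to 1.7 times needs only the uptake assumption and an inert plan. That the SAP's household plan is the protocol's infection control plan is an inference, though a well-supported one. This should be fixed, but the current text does allow a correct analysis.

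**What to change.** 1. In the SAP's Predictor Variables and Analysis for Aim 4, name randomised arm as the main predictor of the treatment effect. In Longitudinal Analysis, write arm and visit into the mixed logistic model and make the 9-month arm contrast, by intent to treat, the primary test. Arm-by-visit terms or the 9-month-only model already planned would both serve. A single arm coefficient shared with baseline rows would not.
2. Restrict adjustment in that model to baseline values.
3. Use household plan, follow-up exposure or infection, and follow-up vaccination only in the structural equation mediation, components-received or variance-partitioning analyses.
4. In Power and Sample Size, state which contrast and which timepoints the figure of more than 80% refers to.

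The cost is SAP wording. No new data are needed and no planned analysis is lost.

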#### **Additional consent provisions for collection and use of participant data and biological specimens**

**{26b}**

Participants will be informed that all assessments and COVID-19 test results will be de-identified. Participant names will be replaced with a unique identification number, which only research staff have access to. Additionally, the consent forms explain how saliva/nasal swab samples may be collected for COVID-19 testing use from enrolled participants in the intervention arm. Only identified positive COVID-19 test results will be reported by name to the NYC Department of Health as part of the NYC COVID-19 test reporting protocol. This research is covered by a Certificate of Confidentiality from the National Institutes of Health (NIH); therefore, the research personnel will not disclose or use information that may reveal participants' names to any federal, state or local civil, criminal, administrative, legislative, or other action, suit, or proceeding, even if a court subpoena is issued. After the study is terminated, participants' data may be used for future research or stored in a data repository without obtaining additional consent.

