### **Intervention description {11a}**

#### *Experimental condition*

The NCFP intervention is delivered by nurses and community health workers (CHWs) as part of a collaborative partnership with households over the course of 5 months. On average, there will be three nurse-CHW home visits to households randomized to the intervention condition per month. Each visit will last for approximately 45 minutes on average.

The NCFP intervention prioritizes provision of intervention content based on three household risk levels: low, medium, and high. This intervention will use an algorithm to determine household-level risk to COVID-19. Low risk is defined by experience of no symptoms and no exposures by all household members. Medium risk is defined by experience of either symptoms (i.e. new cough, chest pain, fever above 100.4°, and/or loss of taste or smell) or an exposure to someone with known or suspected COVID-19 by any household member. High risk is established when a household member has a confirmed positive COVID-19 test. The algorithm will be informed by self-report of symptoms and exposures through a nurse hotline that is available for households placed in the intervention arm to use.

Additionally, nurses will conduct weekly phone screenings to continue monitoring household symptoms and exposures. For households that are at low risk, the intervention delivery team will provide the standard intervention content, which consists of (1) development and follow-up of an infection control plan tailored to the unique circumstances of the household, (2) printed NCFP family materials, (3) offer of monthly routine Polymerase Chain Reaction (PCR) COVID-19 test (self-administered saliva test), (4) provision of PPE (masks, hand sanitizer, gloves) and a thermometer, and (5) navigation to at-home or community-based COVID-19 vaccination services, as well as health, social welfare, vocational,

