### **Implementation {16c}**

Households that are enrolled into the study will be entered into the REDCap database, which automatically assigns a study ID. REDCap assigns the household study ID to either the experimental or control condition using the pre-generated and coded sequence. After completion of the baseline assessment (assessors are blinded), the REDCap data manager notifies the NCFP intervention team of new households that have been assigned to the experimental condition. The intervention team then contacts the household to begin the NCFP intervention program.

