#### Data collection and management

#### **Plans for assessment and collection of outcomes {18a}**

Data will be collected at eight time-points: baseline, monthly during months 1-6 of the study, and at 9 months post-baseline. Participants will complete self-reported surveys that assess basic demographics such as birthdate, age, gender, race/ethnicity, educational attainment, etc. In addition to collecting basic demographics, the study surveys will contain items and scales from the PhenX Toolkit and the NIH Disaster Response website. These survey items and scales will assess participants' household-level

COVID-19 routine testing, household-level COVID-19 indicated testing, COVID-19 vaccine uptake, adoption of COVID-19 control measures, household-level mutual aid capacity, and seasonal influenza vaccine uptake. All survey items developed by our team will be shared with the Rapid Acceleration of Diagnostics Underserved Populations (RADx-UP) Coordination and Data Collection Center and made public. Data will be collected via tablets that will be programmed in REDCap. Surveys are available in English and Spanish to facilitate, survey data collection. The survey may be self-administered or, in the case of low literacy or lack of familiarity with electronic devices, data collection staff will read prompts and record survey responses onto the tablets. Mode of administration will be recorded for later analysis of potential bias. To reduce social desirability bias, CHWs and nurses who deliver the NCFP intervention will not take part in the data collection process. Rather, data collection will be conducted by dedicated staff who are trained in survey research methods and human subject protections, including confidentiality. Additionally, social desirability tendency will be assessed using designated items in the study surveys. Furthermore, we will record participation rates for each household by member.

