### **Confidentiality {27}**

To protect the integrity of the participants' data, the following procedures will be followed. First, all participants enrolled in the study are assigned a random code number. This code number is used on all information collected from participants, including consent forms, surveys, and biological specimen results. Participants will never be identified by name on consent forms, surveys, and biological specimens. No other information that would disclose the participant's identity will be found on any assessment or notes. We will maintain a list of participants with links between identifying information and code numbers. Only the Investigative Team will have access to these lists, which are kept in on a password protected computer system. All data will be stored in locked files or on password protected

computers in the Principal Investigators' and project statistician's offices. As part of the informed consent process, participants will also be informed that all information they provide in interviews is confidential with the following exceptions: (1) If they are in imminent danger of committing suicide or homicide, the appropriate local agency will be contacted and (2) if they are physically or sexually abusing someone, the appropriate local agency will be contacted.

All project staff must complete certain levels of training before working on the project. Study staff also sign confidentiality statements that specify that if the participants' confidentiality is breached unintentionally, then study staff members will follow the procedures for reporting this breach to the Principal Investigators. The confidentiality statement also states that unintentional or deliberate violations of participants' confidentiality may result in demotion or termination depending upon the severity of the event. Personnel also participate in training with the Investigative Team regarding data safety, confidentiality of participants, limits of confidentiality, and proper administration of the study protocol. We estimate that 40 hours of training will be completed by all project staff.

**Plans for collection, laboratory evaluation and storage of biological specimens for genetic or molecular analysis in this trial/future use {33}**

Saliva/nasal swab samples from participants in the experimental condition may be collected for COVID-19 tests. These samples will not be used for analysis or stored for future use.

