Measurement error. Where possible, we will adopt analytic strategies that explicitly model measurement error, such as using SEM with multiple indicators. For single indicator SEM, measurement error can be modeled by fixing error variances of measures at *a priori* specified values that map onto their reliability as suggested by previous research [8,9]. If it is a multi-item measure, we can create multiple indicators using split-half methods. When we cannot formally model measurement error, we will take care to recognize biasing effects of measurement error when interpreting the results of statistical analyses.

Aim 5 is to use FDA-authorized tests, characterize the community and household epidemiology of SARSCoV2/COVID-19 including prevalence of current infection, incidence of new infection,

symptomatic illness, accessing care, hospitalization and mortality.

Analysis for Aim 5

To address Aim 5, we will estimate current infection using SARS-CoV2 RNA testing of baseline specimens from the intervention group. Incidence of new infection per 100 person-months will be estimated from the results of repeat voluntary in-home RNA and antigen testing (intervention group) and approximated from self-reported results of repeat voluntary tests in the controls. Occurrence of symptomatic illness, accessing COVID-19 care, hospitalization and mortality will be measured in both groups by self-report from family members. Qualitative methods will use a grounded theory approach in which ethnographers identify key themes for further inquiry and analyses and contribute to quantitative data triangulation.

Aim 6 is to (with our community and scientific advisory boards,) develop pilot projects that will address knowledge and implementation gaps that are uncovered as new diagnostic testing is developed and as the investigative team and community partners work together to address Aims 1-5.

Analysis for Aim 6

The analysis plans for Aim 6 will be developed for projects as appropriate.

Power and Sample Size.

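### SAP Aim 5 relies on baseline specimens that the protocol does not schedule; as described, the data give RNA positivity among those who accept a first in-home test after allocation, not baseline or community prevalence

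*SAP*

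**What the plan says.** The SAP's Aim 5 is to "characterize the community and household epidemiology of SARSCoV2/COVID-19 including prevalence of current infection, incidence of new infection", among other things. Its analysis section says "we will estimate current infection using SARS-CoV2 RNA testing of baseline specimens from the intervention group". The next sentence bases incidence on repeat in-home tests, which it calls voluntary. It does not say whether the baseline specimen is voluntary, when it is taken or by whom.

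The protocol describes the study assessments in item {18a}: "Data will be collected at eight time-points: baseline, monthly during months 1-6 of the study, and at 9 months post-baseline", and "Participants will complete self-reported surveys that assess basic demographics such as birthdate, age, gender, race/ethnicity, educational attainment, etc". No specimen is listed there. The same item keeps nurses and community health workers out of data collection, and item {17a} blinds the data collection staff to allocation.

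Specimens appear in the consent provisions {26b}, where "saliva/nasal swab samples may be collected for COVID-19 testing use from enrolled participants in the intervention arm", with no time point. RNA testing appears in the Intervention description {11a}, as part of the standard content: "offer of monthly routine Polymerase Chain Reaction (PCR) COVID-19 test (self-administered saliva test". Under Implementation {16c}, the intervention team is told of a household after the baseline assessment is complete, and "The intervention team then contacts the household to begin the NCFP intervention program".

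**The concern.** The SAP names a quantity measured at baseline, while the protocol's only RNA test comes later, after allocation, and only from people who say yes. A reader of the results would take the figure as the prevalence of current infection at study entry and, given the wording of Aim 5, as saying something about the community.

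Two features separate the available figure from that one. The first is selection: the decision to accept may depend on symptoms, known exposure or a recent positive result, so the direction of the error is unknown. The second is timing: no interval between the baseline survey and the first PCR is given, and in an epidemic that moves quickly the interval can change the value.

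Neither document says how declined tests are handled. The SAP's missing-data section deals with unanswered questions and attrition, not with offers of a test that were refused.

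**Working it through.** The plan gives no prevalence, uptake or precision for Aim 5, so there is no figure to reproduce. The check is mainly one of sequence.

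**Order of events**

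1. The household is enrolled. In protocol {16c}, REDCap assigns the arm when the household is entered; in the SAP's Randomization section, allocation follows the baseline assessment.
2. Blinded data collectors carry out the baseline survey ({16c}, {17a}, {18a}).
3. The data manager notifies the intervention team, which contacts the household ({16c}).
4. The team offers a monthly PCR ({11a}); some members accept.

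On either version of step 1, the staff at step 2 could not take specimens from the intervention arm alone. Either allocation has not happened or they do not know it. Item {5d} also keeps the data collection and intervention teams apart. The other in-home tests in {11a}, for medium- and high-risk households, are rapid antigen tests and not RNA tests. On this text the earliest RNA result is at step 4.

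**Selection (illustration; prevalence and relative acceptance are assumptions)**

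Let p be the true prevalence and r the acceptance of infected members relative to uninfected members. The overall acceptance level cancels:

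positivity among acceptors = p·r / (p·r + 1 − p)

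With p = 0.05:

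- r = 0.5: 0.025 / 0.975 = 2.6%
- r = 1: 0.050 / 1.000 = 5.0%
- r = 1.5: 0.075 / 1.025 = 7.3%

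**Bounds with no assumption about who declines**

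If a share u is tested and 5% of those are positive, prevalence in the whole arm lies between 0.05u and 0.05u + (1 − u). The values of u are assumptions.

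- u = 0.9: 4.5% to 14.5%
- u = 0.7: 3.5% to 33.5%
- u = 0.5: 2.5% to 52.5%

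**Sampling error**

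The sample size section implies 100 × 2 = 200 intervention members. The SAP's Design section gives 400 individuals, which at 2:1 is 400 × 2/3 ≈ 267. The upper limit of 0.3 stated for correlation within a household, borrowed here for infection status, gives a design effect of 1 + (2 − 1) × 0.3 = 1.3. With everyone tested and 5% positive, the 95% half-width is:

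- n = 200: 1.96 × √(0.05 × 0.95 × 1.3 / 200) = 3.4 points
- n = 267: 1.96 × √(0.05 × 0.95 × 1.3 / 267) = 3.0 points

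At an assumed 60% acceptance, 200 × 0.60 = 120 are tested. Six positives (5%) then give a Wilson 95% interval of 2.3% to 10.5% before clustering. None of these intervals includes the selection error.

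**The case against.** The strongest reply is that the baseline specimen simply means the first in-home test. The SAP sets it beside repeat tests in the same arm, which makes that a natural reading, and a figure from first tests can be computed. The protocol's silence is also not proof: the consent text gives no timing, the flow diagrams are not available here, and the protocol's objectives do not include Aim 5. This stands in part. A reader might infer that no early specimen exists, or that nothing can be derived, and the documents do not support either statement. But on the first-test reading the time point is still undefined and the figure still describes acceptors only, so the same edit is needed.

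A reader might also see a contradiction in protocol item {33}, which says of the samples that "These samples will not be used for analysis or stored for future use". That sentence answers a heading on genetic or molecular analysis and future use. Items {12} and {19} treat in-home tests and specimen results as study data. It does not conflict with Aim 5 and needs no amendment.

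Three further points are fair. Restricting the estimate to one randomised arm does not by itself bias a prevalence measured before the intervention could act. The community wording belongs to the whole aim, while the analysis sentence does name the intervention group. And weighting for acceptance on baseline variables could not remove selection on symptoms or infection that arise by the test date, and would be unstable with few positives.

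**Conclusion.** The concern holds in this form: the SAP depends on a baseline specimen that the protocol neither schedules nor defines. The testing that is described supports only RNA positivity at the first accepted in-home PCR, among intervention members who accepted. It does not support a baseline or community prevalence.

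This rests on the text as available. It would change if the sponsor could show a specimen collected at baseline under a procedure not described in either document.

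The 2.6% to 7.3% range for a true 5% illustrates how far selection could move the figure. It is not an estimate, because neither prevalence nor acceptance is given. Aim 5 is descriptive: the primary outcome and its power are untouched. The change is still worth making, because it alters what Aim 5 can conclude.

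**What to change.** In the SAP's analysis for Aim 5:

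- Replace the reference to baseline specimens with the first accepted in-home PCR, and state a window counted from the baseline assessment.
- Name the parameter as RNA positivity at that test among intervention members who accepted.
- Report the numbers offered and accepted, the distribution of days from baseline, and a confidence interval that allows for clustering within households.
- Do not present the result as community prevalence.

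An estimate weighted for acceptance, using baseline symptoms, exposure, prior infection and age, is at most an optional sensitivity analysis, with the limits given above stated beside it.

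The cost is SAP wording, a log of test offers and acceptances, and a narrower Aim 5 claim. Recruitment opened on 23 July 2021 and the SAP is dated 07/12/22, so offers to households already visited may have to be recovered from visit records. Where they cannot be, use all enrolled intervention members as the denominator for uptake and say so.
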